Description of Study Design:	
The study will be an open-label, crossover study over 10 weeks (n=12 healthy subjects) with one week washout period between studies.
 
The study contain six procedure days:
 
• Procedure Day 1: RLD topical gel containing 0.75% metronidazole to be applied for 25 h. Blood samples obtained on Procedure Day 1 and 2.• Procedure Day 3: Generic topical gel containing 0.75% metronidazole to be applied for 25 h. Blood samples

obtained on **Procedure Day 3 and 4.**

- **Procedure Day 5:** Generic topical cream containing 0.75% metronidazole to be applied for 25 h. Blood samples obtained on **Procedure Day 5 and 6.**

A) *Pharmacokinetics*

Each subject will be his/her own control and each subject will sign an institutional review board–approved consent form explaining the purpose, nature, risks, benefits, and duration of the study. The study will be conducted in accordance with good clinical practice guidelines and with the ethical principles originating in the Declaration of Helsinki.

The subject's skin in the area of application (upper arm) will be relatively free of hair before gel or cream application. Blood samples (approximately 5 mL (1 tsp) each) will be drawn in BD vacutainer tubes. On Procedure Day 1, 2, 3, 4, 5 and 6, blood samples will be obtained as follows:

- Within 60 min pre-gel/cream application and then during wear, up to 25 h.

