2 BACKGROUND INFORMATION AND SCIENTIFIC RATIONALE

2.1 Background Information

Generic drugs are approved based upon bioequivalence (BE) testing, and with respect to oral drug delivery, the accepted BE approach is relatively straightforward and is principally based on matching blood level profiles. In some cases, in vitro dissolution tests can be done to help determine the bioequivalence of an oral dosage form. For topical drug products in the United States, with the exception of corticosteroids and a few other products, a comparative clinical endpoint study is often necessary for approval of a generic product or for replacement of an approved dermatological drug product with one that has major changes. Comparative clinical trials are relatively insensitive, time-consuming and costly. It is especially difficult to gain the adequate statistical power needed to evaluate bioequivalence for some dermatological conditions, and can require a large number (i.e., hundreds^{1,2}) of subjects.

This study supports FDA's continuing effort to identify the most accurate, sensitive, reproducible and efficient methods to evaluate topical dermatological drug products.

The model drug for this study is metronidazole, which is available in different topical formulations, gel, cream and lotion, approved by the United States FDA. The metronidazole gels and cream have been chosen for this study because the therapeutically equivalent metronidazole gels will be used to evaluate BE in vivo. The metronidazole cream is being used as the non-BE control for this project.

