3 OBJECTIVES

3.1 Study Objectives

- 1) Generate human PK data by collecting data following the application of three metronidazole formulations: RLD and generic metronidazole gel, 0.75% and generic metronidazole cream, 0.75%. This data will be used to assess the bioequivalence of these products or lack thereof.
- 2) To develop in vitro/in vivo correlation (IVIVC) models for dermal products. PK data from this study as well as in vitro data collected elsewhere from IVPT studies will be used to develop IVIVC models which could provide a surrogate for conducting clinical endpoint studies (required to demonstrate bioequivalence of dermal products).

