5.2 Final Analysis Plan

The objective of this study is to determine PK parameters (C_{max} , AUC) of metronidazole in healthy adults after using metronidazole 0.75% gels or cream.

Student's t-test or Analysis of variance (ANOVA) followed by post-hoc Bonferroni test will be used, where appropriate, for comparing the differences in the means of the PK parameters and significant differences will be declared at $p < 0.05$.

If metronidazole PK concentrations are found to be non-normally distributed, then we will examine Box-Cox transformations (e.g., log, square-root, etc.) that can achieve normality. If no transformation can achieve normality, then will use permutation tests to compute empirical p -values, and will use the bootstrap to compute standard errors and confidence intervals that account for within-person correlation.

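### Section 5.2 does not fix the scale or effect measure for Cmax and AUC in advance, and no branch commits to a test/reference ratio with a confidence interval

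*Combined protocol and SAP*

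**What the plan says.** Section 5.2 (Final Analysis Plan) is the only inferential text. It has three steps.

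- Default: a t-test, or ANOVA with Bonferroni, for "comparing the differences in the means of the PK parameters", with significance at p < 0.05. Transformation is conditional, so the default is the untransformed scale.
- Change of scale: "If metronidazole PK concentrations are found to be non-normally distributed, then we will examine Box-Cox transformations (e.g., log, square-root, etc.) that can achieve normality". No normality test, threshold, unit of checking or order of search is given.
- Last fallback: "If no transformation can achieve normality, then will use permutation tests". In this step only, the plan "will use the bootstrap to compute standard errors and confidence intervals that account for within-person correlation". It does not say which quantity the interval is for, or at what level.

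The stated use is in section 3.1: "This data will be used to assess the bioequivalence of these products or lack thereof". Section 2.1 adds that the "therapeutically equivalent metronidazole gels will be used to evaluate BE in vivo". The Protocol Summary gives a crossover in 12 healthy subjects and says "Each subject will be his/her own control".

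**The concern.** A reader assessing bioequivalence needs the size of exposure from one product relative to another, with its uncertainty, in the same form for Cmax and AUC. Section 5.2 promises a p-value on a scale settled after the data are seen. Depending on the normality check, the result could be a difference in concentration units, a difference of square roots, a log difference, or a permutation p-value with a bootstrap interval for something unspecified. Only some of these say how much more or less drug one product delivers. Nothing elsewhere in the document fixes the scale or promises a ratio.

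What is at stake is whether the result can be interpreted for its stated purpose, and whether its form was chosen before the data were known.

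**Working it through.** The plan gives no variability, power, margin or interval width, so it has no figure of its own to reproduce. The check is a reading of the branches, followed by illustrations under stated assumptions.

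**1. Inputs from the document.** 12 subjects, three products, crossover (Protocol Summary); p < 0.05 and the three-step rule (section 5.2); 13 post-application sampling times (section 5.1). Every CV, SD, correlation and normality test below is an assumption.

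**2. What each scale delivers.** Let d be the test-minus-reference difference on the analysis scale and R the reference value.
- Raw: T/R = 1 + d/R. A ratio needs R and its uncertainty; the plan does not say it will be formed.
- Square root: T/R = (1 + d/√R)². The same d gives different ratios for different R.
- Log: T/R = exp(d). The ratio follows from d alone, and so does its interval.
- Permutation and bootstrap: a p-value, and an interval for an unnamed quantity.

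Only the log scale gives a within-subject ratio directly, and it is one example in an open list.

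**3. What the trigger acts on.** Section 5.2 compares PK parameters but checks PK concentrations.
- Taken literally, the check covers up to 13 × 12 × 3 = 468 correlated serum values and could give one transformation for everything. This reading was not simulated, because the document gives no concentration profile.
- Taken as a check on each parameter, the scale depends on details left open. With log-normal values and Shapiro-Wilk at 5%, non-normality is flagged in 14% of sets of 12 and 42% of sets of 36 at CV 30%, and in 28% and 75% at CV 50%. The Box-Cox power estimated from 12 values (true value 0, the log) has a 5th to 95th percentile range of -1.72 to 1.58 at CV 30%. Over 12 readings of the rule (within-subject CV 25%, between-subject CV 40%, Cmax–AUC correlation 0.9), the two parameters end on different scales in 18 to 54% of simulated trials.

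**4. Error rates.** Share of true differences missed with a fixed scale, 12 subjects, alpha 0.05/3 (Bonferroni for three comparisons), 100,000 simulated trials:
- Log-normal, CVs 25%/40%, true ratio 0.70, paired: 24.6% log, 36.0% raw.
- Same data, unpaired: 81.2% log, 83.9% raw.
- Additive-normal, means 1 and 0.7, paired: 8.8% log, 3.4% raw at within/between SD 0.15/0.20; 55.6% log, 44.2% raw at 0.25/0.20.

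With no true difference, the data-driven rule rejects in 4.3 to 5.0% of trials at alpha 0.05.

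**5. What a fixed log analysis would report.** For a paired comparison with n = 12 and an observed ratio of 1.00, the 90% interval (level assumed) is exp(± t(0.95, 11) × s × √(2/12)), with s = √ln(1 + CV²). At within-subject CV 30%, s = √ln(1.09) = 0.294. The half-width is 1.796 × 0.294 × 0.408 = 0.215, giving 0.806 to 1.240. At CV 20% the interval is 0.865 to 1.156, and at 50% it is 0.707 to 1.414.

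**The case against.** The strongest case on the other side has four parts.

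- **The trigger names concentrations.** A reader might infer that Cmax and AUC will be put on different scales. The text does not support that: it follows only if each parameter is checked separately, and a single check on concentrations could give one scale for both. This stands. But on the literal reading the plan checks one quantity and tests another, which also needs correcting.
- **There is little inferential harm.** A reader might infer that letting the data choose the scale inflates false positives or costs power. The document gives no distribution or variability from which to show either. In the illustrations false positives stay near nominal, the power ordering reverses with the distribution, and with unpaired tests scale hardly matters. Section 5.2 does not say its tests are paired. This stands in full.
- **A ratio can be computed anyway.** True: a ratio of arithmetic means could be formed from the raw data. In the central log-normal setting it differs from the geometric mean ratio by a median of 2.6% (95th percentile 8.3%). What is lost is commitment, not information. But nothing obliges the analyst to report a ratio, or the same one for both parameters.
- **The study is research, not an approval application.** Section 5.2 states its aim as determining PK parameters, and section 2.2 aims at an in vitro/in vivo correlation. That lowers the stakes. It does not remove the mismatch with section 3.1, nor the need for an interpretable reference dataset.

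**Conclusion.** The point holds as one of interpretability and pre-specification. Section 5.2 leaves scale and effect measure to an undefined check, no branch commits to a test/reference ratio, and confidence intervals are named only in the last fallback. This rests on the text alone and needs no simulation. It should be corrected, but it does not invalidate the study.

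Its size cannot be stated as a loss of power or an excess of false positives. The 18 to 54% scale disagreement illustrates what is possible under a per-parameter check with assumed inputs; it does not predict what this trial will do.

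Two further inferences should be resisted. It would be wrong to say that the plan omits confidence intervals, since the bootstrap step names them. And fixing the scale would not make this a test of bioequivalence: the document gives no equivalence criterion, and that is a separate point.

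**What to change.** In section 5.2, replace the normality trigger and the Box-Cox search with a pre-specified within-subject analysis of ln(Cmax) and ln(AUC), with subject and product as factors. Report geometric mean ratios with confidence intervals, at a stated level, for all product comparisons. State a rule for zero or unquantifiable values, which cannot be logged. Keep residual plots and the planned permutation and bootstrap analyses as sensitivity analyses, done within subject; a bootstrap ratio of arithmetic means can be one of them.

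The cost is wording only, with no extra data. The downside is some loss of power if the data are in fact additive-normal: in the two assumed cases above, 8.8 − 3.4 = 5.4 and 55.6 − 44.2 = 11.4 percentage points.
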